Some participants may also have co-occurring conditions which would prevent them from participation in the imaging arm of the study (claustrophobia; presence of metal in the body). These participants will be enrolled in the study but will not complete imaging procedures. A chart review of PIRATE participants to date indicates that approximately 20% of veterans enrolled in PIRATE may have such exclusionary criteria: roughly 17% report pacemaker or other implanted metal objects or devices incompatible with MR scanning. Thus, the participant sample used to address the neuroanatomical hypotheses proposed under Specific Aim 1 may be smaller than the sample contributing data the other proposed analyses. Under the worst case scenario of no overlap between these imaging-related exclusionary criteria and those described in the preceding paragraph, we expect to obtain a sample size of 40 participants (50 minus 20%) to conduct the proposed imaging-related analyses. As described in section C.3.1.3 below, this sample size should be sufficient to detect the relationships relevant to the neuroanatomical hypotheses.

C.2 Procedures

The schedule of procedures for participants enrolling in the study is summarized in the flowchart in Figure 4. Participants enrolling in the research study will receive a single pre-treatment structural MRI and a battery of cognitive assessments at program entry (see section C.2.3 below). They will also have their performance on standardized measures of naming and other language functions assessed repeatedly throughout the protocol (see section C.2.2 below), and they will receive an intensive dose of a treatment (SFA) designed to target lexical-semantic processes (see section C.2.1 below). Participants' performance on treated and untreated lexical items will be probed three times weekly, to assess acquisition and generalization and to decide when participants will move to a novel set of treatment exemplars.

Half the participants will be randomly assigned to a delayed-treatment condition. The purpose of this condition is to provide an additional measure of experimental control, to ensure that any observed improvements are not due simply to the social contact afforded by the residential component of the treatment program. Previous work [7] has found that simple exposure or engagement in the absence of specific therapy

[figure not shown]

Figure 4: Testing and treatment procedures for study participants

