Treatment will be conducted five days a week (Monday through Friday) across two daily 120-minute intervals, one morning session and one afternoon session, for a total of 4 hours of treatment per day and 20 hours per week. A 20-minute break will be provided within each 120-minute treatment interval and a 120 minute break will be provided between each 120-minute treatment interval. Time in treatment will be recorded in daily logs, as will the number of exposures to each training exemplar, the number of treatment trials, and the number of features (both novel and recurring) generated for each item on a given treatment trial. In addition, participants will be engaged in planned social and recreational activities on the weekends, such as visits to

local sites and events (like a baseball game). These activities will not target or specifically stimulate language function or the skills trained in therapy.

As indicated above, half the participants will be enrolled in treatment immediately upon their arrival at VAPHS, and half will be entered into the delayed-treatment condition. Participants assigned to the delayed-treatment condition will arrive one week prior to treatment initiation. During this week, they will be in residence at the HJ Heinz campus and engage in non-language recreational activities in 2 two-hour sessions per day (the same schedule as will be followed during treatment). These activities will be led by a study staff member experienced in working with stroke survivors. The morning session will consist of recreational activities regularly conducted at the H.J. Heinz campus, listed in Table 6 below:

Billiards	Recreational Hall, H.J. Heinz campus
Physical exercise	Gym, H.J. Heinz campus
Ceramics, other visual arts	Art Studio, H.J. Heinz campus
Puzzles and board games	Recreational Hall, H.J. Heinz campus

Table 6. Non-language-focused recreational activities for participants enrolled in delayed-treatment condition

The afternoon session will consist of either complementary activities drawn from Table 6 or off-site visits to local destinations. While these sessions will afford multiple social contacts and interactions, typical of structured recreational programs, they will not target specific speech and language behaviors. Participants randomized to the delayed treatment group will receive probes (naming and PNT and other assessments [CAT, discourse measures]) on the same schedule as the no-delay group.

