The first analysis will evaluate whether the social contact associated with PIRATE participation results in improved performance on study measures, independent of any actual aphasia treatment. We will use a multivariate mixed model to test whether there are any differences between the immediate-treatment and delayed-treatment groups at the initiation of treatment, and whether there is any group-by-time interaction suggesting a positive effect of the delayed treatment week. The dependent variables will include performance on treated and untreated naming probes and PNT short forms.

If this analysis finds no significant differences between the groups, it will suggest that any observed treatment gains can be attributed to the SFA treatment rather than general effects of the social contact associated with PIRATE. In this case, the two groups will be collapsed for further analysis. In the unexpected event that this analysis finds a significant difference favoring the delayed treatment condition, it will suggest that observed treatment gains should be attributed to the combination of SFA and the socialization inherent in a residential treatment program, rather than to SFA alone. In this case, we will use the data to estimate the size of the socialization effect and statistically control for it in subsequent analyses, where possible.

C.3.1 Psycholinguistic, cognitive, and neuroanatomical predictors of treatment response

The primary dependent variable for analyses relevant to Specific Aim 1 will be the proportion of correctly-named treated stimuli at study exit (post-treatment), minus the proportion of correctly-named treated stimuli at study entry (pre-treatment). This difference score provides the simplest measure of naming treatment response. Supplementary analyses may be carried out using a related dependent variable, the percentage of possible naming improvement^[10]. This is a derived measure which divides the simple pre-post difference score

by the difference between pre-treatment naming performance and ceiling performance (100% accuracy minus observed pre-treatment accuracy). This measure helps correct for observed differences in baseline accuracy.

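### The planned arm comparison at treatment start contains no SFA effect, and the concurrent first-week SFA-versus-recreation contrast is not prespecified

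*Combined protocol and SAP*

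**What the plan says.** Section C.2 states that "Half the participants will be randomly assigned to a delayed-treatment condition", and gives the purpose: "to ensure that any observed improvements are not due simply to the social contact afforded by the residential component of the treatment program". Under C.2.1, "Participants assigned to the delayed-treatment condition will arrive one week prior to treatment initiation". They spend that week in residence, with recreation in two daily two-hour sessions that mirror the treatment timetable, and are assessed "on the same schedule as the no-delay group". Whether that schedule is counted from arrival or from the start of treatment is not stated.

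The opening of C.3 describes the analysis of this randomisation. A multivariate mixed model will "test whether there are any differences between the immediate-treatment and delayed-treatment groups at the initiation of treatment". Its outcomes are treated probes, untreated probes and PNT (Philadelphia Naming Test) short forms. A second question put to the same model is "whether there is any group-by-time interaction suggesting a positive effect of the delayed treatment week". Two results are provided for. If there is no significant difference, gains are taken to be attributable to SFA and the arms are pooled. If a difference favours the delayed arm, gains are attributed to SFA plus socialisation, and the socialisation effect is estimated and controlled for where possible. The time points in the interaction are not defined.

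**The concern.** In the first residential week the immediate arm receives residence plus SFA, and the delayed arm receives residence plus recreation on the same timetable. Randomisation makes this a concurrent comparison of SFA with social contact, and no section asks for it. The comparison that is specified falls before either arm has had SFA, yet its null is given the job of attributing gains to SFA. Finding no effect of one residential week removes one rival explanation. It does not show that the gains over the following four weeks come from SFA.

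The other randomised comparison, two versus four weeks of treatment in C.3.2, has SFA in both groups and cannot fill the gap. As written, attribution to SFA rests on within-subject controls and on accepting a null with no margin and no stated power.

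**Working it through.** **Inputs**
- Sample: 50 completers (C.1), half randomised to each arm (C.2), so 25 per arm.
- SD of naming change: 9 and 17 percentage points, from two groups of four over full treatment courses (A.1.1). Using them for one-week change is an assumption.
- Treatment starts with one set of 10 of the 40 training items (C.2.1).
- No power is stated for the arm comparison. The nearest figure is 0.82 for a 20-point difference between impairment groups of 12 and 12 (C.3.1.1).

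**1. The plan's own figure.** With SD 17 and two-sided 5% (assumed; no alpha is given), power = Φ(20 / (17 × √(2/12)) − 1.96) = Φ(2.88 − 1.96) = 0.82. It reproduces with the larger SD and a normal approximation. With the pooled SD, √((17² + 9²)/2) = 13.6, it would be 0.95. This only fixes the SD scale.

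**2. What each contrast estimates.** Let S be the effect of one residential week, T of one week of SFA and P of one week of probing, taken as additive.

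| Time | Immediate | Delayed | Difference |
|---|---|---|---|
| Treatment start | 0 | S (+P if probed in the recreation week) | delayed − immediate = S (+P) |
| End of residential week 1 | S + T + P | S (+P if probed in the recreation week) | immediate − delayed = T, or T + P if the delayed arm was not probed |

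T is absent from the first row.

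**3. Simulation.** 25 per arm, SD of change 13.6, P = 0, t-test on change from initial evaluation, 20,000 replicates. Entries are the proportion significant at 5%.

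| S | T | Treatment-start contrast | Week-1 contrast |
|---|---|---|---|
| 0 | 0 | 4.8% | 4.7% |
| 0 | 10 | 4.9% | 72.5% |
| 0 | 20 | 4.9% | 99.9% |
| 5 | 10 | 24.9% | 71.6% |

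The planned test behaves the same whether SFA does nothing or adds 20 points. The last row shows that a true 5-point residential effect would be missed about three times in four. With SD 17 the power for that effect is 0.18.

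**4. Precision of the week-1 contrast.**
- 95% CI half-width = t(0.975, 48) × SD × √(2/25) = 2.011 × 0.283 × SD = 0.569 × SD. This gives 5.1, 7.7 and 9.7 points for SD 9, 13.6 and 17.
- Difference detectable with 80% power (normal approximation) = (1.960 + 0.842) × 0.283 × SD = 0.792 × SD. This gives 7.1, 10.8 and 13.5 points.

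**5. Choice of items.** If only the first set is treated in week 1 and the other 30 items do not move, a gain of T on that set averages to T × 10/40 = T/4 over all 40 items. The SD of a 40-item score may also fall, so the loss of power need not be fourfold.

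**6. Availability of data.** All 361 pictures are named three times at the initial evaluation (C.2.1), which gives both arms a common baseline. Probes are given at treatment initiation (C.2.2), which for the delayed arm is the end of the recreation week. The last probe of each treatment week is the weekly measure (C.3.2), which gives the immediate arm its end-of-week-1 value.

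**The case against.** The planned contrast answers the question C.3 sets for it: whether contact improves performance in the absence of treatment. It is randomised and serves the purpose in C.2. A reader might infer that it is simply the wrong analysis. The documents do not support that. The week-1 contrast has a different estimand and belongs beside it.

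A reader might also infer that the evidence for SFA is otherwise uncontrolled pre-post change. It is not. There is a pre-treatment interval with no change predicted (C.3.2), unrelated untreated items and nonword repetition (C.2.2), item sets introduced in sequence (C.2.1), and scoring blind to time point (C.2.2). These controls have limits: A.1.1 reports generalisation to unrelated items in 12 cases, and no analysis in C.3 uses nonword repetition. None is a randomised comparison with contact.

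A third tempting inference is that, with time counted from arrival, the rule would reach the opposite of the right conclusion. The wording disfavours that clock, because the interaction is read as a benefit of the delay week and only a difference favouring the delayed arm is provided for. On an arrival clock, a detected SFA benefit would favour the immediate arm, a result neither branch covers.

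Three cautions stand. A delayed-arm probe at arrival is not established. SFA is individual work with licensed clinicians, whereas recreation is led by a study staff member, so the type of contact is not identical. The SDs are borrowed, and the 20-point criterion in C.3.1.1 concerns impairment groups, so it is no benchmark for this contrast.

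**Conclusion.** The concern holds as an omission and an over-reading of a null. The treatment-start comparison is a valid randomised estimate of one residential week (contact plus any extra probing). Because it contains no SFA effect, a non-significant result cannot by itself support attributing gains to SFA. The one randomised comparison of SFA with social contact is not prespecified, although the probes for it appear to exist.

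With 25 per arm and an assumed SD of one-week change of 9 to 17 points, it would be estimated to within about 5 to 10 points. If the delayed arm is not probed during the recreation week, the contrast also includes a difference in probe exposure. Predictors and dose-response are the trial's main aims and do not depend on this analysis, so it should be added but does not undermine the design.

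**What to change.** In the opening of C.3:
- Define the time origin and the time points in the model, and state whether the delayed arm is probed at arrival and during the recreation week.
- Prespecify the arm difference at the end of the first residential week. Use each participant's designated first 10-item set in both arms, with the PNT form as a second outcome. Adjust for the common initial-evaluation score, or for the arrival score if the delayed arm is probed at arrival. Report a 95% CI.
- Keep the treatment-start comparison as the estimate, with CI, of the contact-plus-probing effect. Remove the inference from its null to SFA efficacy.
- State that the randomised evidence covers week 1 only and, if the delayed arm is not probed in the recreation week, that the contrast includes probe exposure.

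The cost is plan wording and a model for each of the two outcomes, on assessments that appear to be scheduled already. The price is a narrower claim: randomised attribution to SFA is limited to the first week, and later gains continue to rest on the within-subject controls.

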hours. All treatment and probe pictures will be selected from the pictures named correctly on fewer than two of those occasions. Four sets of 10 items each will be selected as potential treatment items, along with four sets of 10 related generalization probe items and four sets of 10 unrelated generalization probe items. For each treatment item, a category coordinate will be selected as a generalization probe item. The unrelated generalization probes will be selected from remaining items belonging to categories not occurring within the treatment set. These items will also be selected to minimize associative and other semantic relationships with items in the treatment sets. Within the constraints of semantic relatedness and baseline performance level, we will balance the treatment and generalization sets for lexical frequency and length.

[figure not shown]

Figure 5. Panel A: Expected score for each of the seven 25-item PNT alternate forms, compared to empirical data of 254 aphasic patients. Panel B: Mean Rasch-scaled score for each of the seven alternate PNT forms, for a subsample of 57 aphasic patients.

C.2.2 Probe stimuli, procedures and schedule

Following baseline assessment of all 361 UCSD CRL items, the 40 items selected for training, 40 related items, and 40 unrelated items will be probed at treatment initiation, three times per week during

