treatment, at program exit, and at one-month follow-up. As an additional measure of within-subject control, we will also obtain baseline measures and weekly probes on the non-word repetition subtest of the PALPA. Generalization of SFA treatment to improved performance on nonword repetition is theoretically possible, but unexpected. The Philadelphia Naming Test (PNT)^[92], a standardized measure of naming performance, will be administered weekly during baseline and treatment phases of the study. In order to eliminate the possibility that observed performance gains on the PNT could be attributed to repeated exposure to the same picture stimuli, we used methods based in item response theory^[93] (IRT) to organize the 175 PNT items into seven equivalent 25-item alternate forms. We accomplished this in the following steps, using data taken from the Moss Aphasia Psycholinguistics Project Database (MAPPD)^[94], which contains item-level PNT response data collected from 254 persons with aphasia. First, we confirmed that a single underlying factor can satisfactorily account for aphasic performance on the PNT. We fit a unidimensional model to the data using NOHARM^[95], and found that fit was excellent (root mean square of the model residuals = 0.010 vs. criterion of < 0.25; Tanaka Goodness of Fit Index = 0.985 vs. criterion of >0.95 for good fit). Next, we fit the data to a 1-parameter IRT model (Rasch) for dichotomous items using WINSTEPS^[96, 97]. We found that all items obtained information-weighted mean-square statistics <1.4, suggesting adequate fit to the model^[98]. We then used the model-estimated item difficulty values to construct the seven alternate forms such that they were of equivalent overall difficulty and gave equivalent expected proportion correct scores as a function of latent naming ability. Panel A of Figure 5 shows the model predicted and empirical raw score for each alternate form as a function of Rasch-scaled latent naming ability, estimated based on the responses to the full PNT. The model curves for the seven forms are essentially identical and well-approximated by the empirical data. We then cross-validated these forms using new data from a subsample of 57 patients who were administered the PNT a second time. For these 57 patients, we computed the latent naming ability score for each alternate form and found that they adequately fit a strictly parallel test model (i.e., had equivalent means, true score variances, and error variances), $\chi^2 = 37.757$ with 32 df, $p = 0.223$. The average correlation between forms was 0.87 (min-max = 0.82-0.93). The means and standard deviations for each of the seven forms are displayed in Panel B of Figure 5.

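### A non-significant delayed versus immediate comparison is read as pointing to SFA rather than social contact, and the plan commits to estimating the contact effect only if the result is significant and favours delay

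*Combined protocol and SAP*

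**What the plan says.** Section C.2 (Procedures) gives the purpose of the delayed-treatment arm: "to provide an additional measure of experimental control, to ensure that any observed improvements are not due simply to the social contact" of the residential programme. Under section C.2.1, participants in this arm arrive one week before treatment starts and spend that week in recreational sessions without language therapy.

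The opening of section C.3 (Data analysis) sets out the test. A multivariate mixed model compares the arms when treatment starts and looks for a group-by-time interaction over the delay week, using treated probes, untreated probes and PNT short forms. Two outcomes have a stated consequence:

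- **Not significant.** "If this analysis finds no significant differences between the groups, it will suggest that any observed treatment gains can be attributed to the SFA treatment", as opposed to social contact. "In this case, the two groups will be collapsed for further analysis".
- **Significant, favouring delay.** "In the unexpected event that this analysis finds a significant difference favoring the delayed treatment condition", gains are to be credited to SFA and socialization together. "In this case, we will use the data to estimate the size of the socialization effect and statistically control for it in subsequent analyses". The plan limits this control to cases in which it is feasible.

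No action is stated for a significant difference favouring immediate treatment. No alpha, sidedness, power, margin or confidence interval is given for this comparison. The sample-size statement in C.1 and the power analyses in C.3.1.1 and C.3.1.3 concern the Specific Aims. The familywise rate of 0.1 in C.3.2 belongs to the Aim 2 pairwise tests.

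**The concern.** A non-significant difference is evidence against a contact effect only to the extent that the data could have shown one. The plan states a decision rule on significance without saying what size of effect the comparison can exclude, and the branch it expects to follow is the one with no commitment to an estimate.

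At stake is whether gains can be credited to SFA rather than to the residential setting. The randomised delay week is the only design element that isolates residential contact from therapy. If the attribution rests on a p-value alone, a reader cannot tell a tight interval around zero from a wide one that also covers a moderate effect.

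**Working it through.** The plan gives no figure for this comparison, so there is none to reproduce. The check asks what a two-arm comparison of this size can show.

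**Inputs**

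- Sample: C.1 expects at least 50 participants to complete all visits. C says half are randomised to delay. This gives about n = 25 per arm.
- Alpha and sidedness: not stated. Two-sided 0.05 is assumed, with one-sided 0.05 as a sensitivity check.
- Outcome: a single continuous outcome is assumed, namely change over the delay week.
- Scale: effects are in units of the between-participant SD of one-week change, because the documents do not give that SD.

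**Precision**

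Half-width of the 95% confidence interval = t(0.975, 2n − 2) × √(2/n) SD

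= 2.011 × √(2/25) = 2.011 × 0.283 = **0.57 SD**

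Even an observed difference of exactly zero would leave effects up to 0.57 SD inside the interval. A positive difference just short of significance would have an upper limit near 0.57 + 0.57 = 1.14 SD.

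**Power**

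Noncentral t with 48 degrees of freedom and noncentrality d × √(n/2) = d × 3.54:

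| | Power at d = 0.5 SD | d for 80% power |
|---|---|---|
| Two-sided 0.05 | **0.41** | **0.81 SD** |
| One-sided 0.05 | 0.54 | 0.71 SD |

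**Sensitivity**

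- *More participants.* If all 58 expected eligible veterans reached this comparison (29 per arm), two-sided power at 0.5 SD would be 0.46 and the half-width 2.003 × √(2/29) = 0.53 SD.
- *Several outcomes.* Approximating the multivariate test by Hotelling's T-squared on three outcomes, each shifted by 0.5 SD (3 and 46 degrees of freedom), gives power of 0.53 to 0.30 for correlations of 0.2 to 0.8 between outcomes.
- *One-sided bound.* After an observed zero, a one-sided 95% upper limit is 1.677 × 0.283 = 0.47 SD. This would just exclude 0.5 SD, but only if the estimate was at or very near zero.

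The last case shows that what can be excluded depends on the estimate and its standard error. The significance verdict carries neither.

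**The case against.** The strongest reply is that little depends on this test. It belongs to neither Specific Aim, the plan calls it an additional control, and the conclusion is hedged with *suggest*. Other controls exist: "As an additional measure of within-subject control, we will also obtain baseline measures and weekly probes on the non-word repetition subtest of the PALPA"; unrelated untreated items are probed; and no significant change is predicted between initial evaluation and program entry. This stands as a limit on severity. None of these bounds the effect of residential contact on naming, however. Nonword repetition is not naming. A rise on unrelated items could itself be SFA generalisation, which section A.1.1 reports in 12 cases. In the immediate arm the pre-treatment interval precedes residence.

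A second reply is that a mixed model with repeated probes may be more precise than a two-sample t-test. That is correct, so the figures above are indicative. It does not repair the rule, because a more precise estimate helps the reader only if it is reported.

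Three stronger readings are tempting, and the documents do not support them:

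- *The plan will withhold the contact estimate after a null result.* It is silent on reporting in that branch, and the planned model produces a group-by-time estimate in any case. What is missing is a commitment to report it.
- *Contact effects of some number of percentage points a week would be missed at a known rate.* The documents give neither the SD of one-week change nor the course length behind the gains quoted in A.1.1. Any such rate would rest on assumptions alone.
- *Pooling the arms is what undermines the attribution.* During the four treatment weeks both arms receive SFA and contact together, so an arm term cannot separate them. The main Aim 1 outcome is each participant's own change from study entry to exit, and arm is randomised, so pooling should not confound the predictor analyses.

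**Conclusion.** The point holds as a fault in the inference rule and in the reporting commitment. With about 25 per arm, a single outcome and two-sided 0.05, power is 0.41 at 0.5 SD, and a null result leaves at least one direction of effect open to 0.57 SD or more. Non-significance alone therefore does not support attributing gains to SFA as against a moderate contact effect. A large effect, at or above about 0.81 SD in the single week, would probably be detected, so the comparison is informative and worth keeping.

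Even a tight interval would speak to one week of contact, whereas treatment takes place over four weeks of residence. The plan does not state this limit beside the attribution.

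Severity is minor to moderate: the aims do not depend on this test, but a headline interpretation of the gains does. The figures rest on the assumed alpha and on the two-sample approximation. The criticism of the rule does not.

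**What to change.** 1. Report the delay-week contact effect, as the group-by-time estimate, with its 95% confidence interval for each outcome in this analysis, whatever its p-value or direction. This also covers a difference favouring immediate treatment.
2. Replace the rule that moves from non-significance to attribution with wording based on the size of contact effect the interval excludes. State that it concerns one week of contact, against four weeks of residence during treatment.

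Optionally, keep randomised arm as a term in the later mixed, ANOVA and regression models in place of pooling on a test. This is a modelling choice costing about one degree of freedom per model, and it does not settle the attribution.

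Items 1 and 2 change only the wording of the analysis plan. They need no new participants, no new data and no formal equivalence test. The downside is that the attribution statement may turn out inconclusive if the interval is wide.
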